7.2.1.1 Reporting a DLT

Any DLT occurring in a patient in the safety lead-in cohort during Cycle 1 must be reported to the Medical Monitor by the Investigator or designee within 24 hours of first knowledge, and to the Innovations Safety Department as an SAE when appropriate (see Section 6.5).

7.2.2 Part B: Expansion cohort

The AZD1775 dose (175 mg BID PO) and schedule (Days 1-3, Weeks 1 and 2, Q 21-days) for the Part B expansion is the dosing schedule that was defined in the Part A safety lead-in.

Part B expansion cohorts will investigate AZD1775 monotherapy in patients with advanced tumour types with molecular biomarkers of interest. The tumour types to be evaluated are:

- **Ovarian cancer** defined as a histologically confirmed diagnosis of epithelial ovarian, fallopian tube, or primary peritoneal cancer refractory to standard therapies or for which no standard therapy exists.
 - Patients with confirmed BRCA wild-type from a prior test conducted by a clinical laboratory that has received international or country specific

certification, who have already received 3 or more prior lines of therapy for advanced disease (recurrent or metastatic).

- Patients with confirmed *BRCA1* and/or *BRCA2* mutation from a prior test conducted by a clinical laboratory that has received international or country specific certification, who have progressed while receiving and/or following treatment with a PARP-inhibitor for advanced disease (recurrent or metastatic).
- **TNBC** defined as histologically confirmed diagnosis of breast cancer that must be triple-negative, defined as minimal or no expression of oestrogen and progesterone receptors (<10% of cells positive by immunohistochemistry [IHC]), and minimal or no expression of HER2 (IHC staining of 0 or 1+ or FISH-).
 - Patients must have already received at least 1 chemotherapy-containing regimen for advanced disease (recurrent or metastatic).
- **SCLC** defined as a histologically confirmed diagnosis of SCLC
 - Patients must have received no more than 1 chemotherapy-containing regimen for advanced disease (recurrent or metastatic) and must have relapsed at least 90 days following that treatment.

All tumour samples will be analysed for a range of cancer-related genes such that clinical response can be correlated to the gene aberrations.

BRCA wild-type is defined as having no evidence of deleterious or suspected deleterious mutation in *BRCA1* or *BRCA2* genes. *BRCA1* and/or *BRCA2* variants that are classified as ‘variants of uncertain clinical significance’ or ‘variants of unknown significance (VUS)’, as well as ‘variants, favour polymorphism’ or ‘benign polymorphism’, are considered to be BRCA wild-type.

Biomarker ‘positive’ cohorts to be analysed include:

- Amplification of at least one of the following genes: *CCNE1*, *MYC*, *MYCL*, or *MYCN* in TNBC or SCLC

TNBC and SCLC biomarker ‘positive’ cohorts to be analysed include amplifications of *CCNE1*, *MYC*, *MYCN* or *MYCL1*.

Biomarker ‘negative’ is defined as the absence of the qualifying amplification for TNBC or SCLC as specified above. There is the potential to recruit and treat up to an additional 20 patients (total N = 50) in the TNBC and SCLC cohorts, to explore additional genetic profiles of interest or gain additional information on the existing genetic profile, based on emerging signals.

Identification of biomarkers of interest based on emerging science is anticipated as the study proceeds. Initially, a retrospective molecular analysis of tumour samples may be performed on approximately the first 15 patients under each tumour type. These patients will be allocated to the biomarker 'negative' or 'positive' cohort retrospectively, once their genetic profile analysis result is available from the central lab. To ensure balance between the biomarker-positive and biomarker-negative cohorts, a switch to prospective molecular analysis at study entry will be required after this point. A QC check of the submitted pathology material will be performed for both groups pre-treatment.

7.3 Restaging during treatment

Tumour assessments will be performed on all patients at Screening (within 28 days of first dose) as outlined in the Study Plan [Table 1](#) and [Table 2](#) until objective disease progression as defined by RECIST v1.1 or other withdrawal criteria is met (see Sections [5.1.1](#) and [3.10](#)). Tumour assessments and restaging will be performed every 6 weeks. Patients continuing study treatment for a minimum of 1 year may have the tumour imaging assessments expanded to every 4 cycles (12 weeks [± 7 days]).

7.4 Labelling

Details are specified in the document explaining the reconstitution procedures and other handling procedures for the investigational product.

7.5 Storage

AZD1775 should be kept in a secure place under appropriate storage conditions. A description of the appropriate storage conditions is specified in the document explaining the reconstitution procedures and other handling procedures for the investigational products.

7.6 Compliance

The administration of all study drugs (including investigation products) should be recorded in the appropriate sections of the eCRF.

7.7 Accountability

Study drug will not be distributed to the study site until the contract is concluded between the study site and AstraZeneca. The Investigational Product Storage Manager is responsible for managing the study drug from receipt by the study site until the return of all unused study drug to AstraZeneca. AstraZeneca will provide the study documents 'Procedures for drug accountability' and 'Procedures for drug storage' which describes the specific requirements. The Investigator(s) is responsible for ensuring that the subject has returned all unused study drug.

7.8 Concomitant and other treatment(s)

All concomitant medications received within 14 days before the first dose of study medication and 30 days after the last dose of study medication should be recorded. Concomitant medications must be recorded in the appropriate sections of the eCRF.

7.8.1 Permitted concomitant medications

Supportive Medication/Class of drug:	Usage:
Anti-emetics (excluding aprepitant [Emend] and fosaprepitant)	Premedication with anti-emetics is mandatory (excluding aprepitant [Emend] and fosaprepitant) as presented in Section 6.8.3.2.
Loperamide (Imodium)	Loperamide (Imodium) is required for the first onset of diarrhoea according to ASCO guidelines (see Section 6.8.3.1).
Medications including but not limited to the following: 
 Bisphosphonates and receptor activator of nuclear factor kappa-B ligand (RANKL) inhibitors (e.g. denosumab). Patients requiring therapeutic warfarin or Coumadin-derivative anticoagulants will be monitored with INR and Prothrombin Time (PT) as clinically indicated. Low molecular weight heparin, rivaroxaban, or equivalent anticoagulant therapy is permitted where clinically indicated. 	Medications may be administered for maintenance of existing conditions prior to study enrolment or for a new condition that develops while on study.

7.8.2 Restricted concomitant medications

The following treatments and the medications listed in [Appendix G](#) should be used with caution while in this study. Any further questions regarding concomitant treatments should be referred to the Medical Monitor.

Restricted Medication/Class of drug:	Usage:
In vitro data suggests that AZD1775 may also be a weak reversible inhibitor of CYP2C19.	Caution should be exercised with concomitant administration of AZD1775 and agents that are sensitive substrates of CYP2C19, or substrates of this enzyme with narrow therapeutic range. Refer to Appendix G for a list of sensitive substrates of CYP2C19, or substrates of this enzyme with narrow therapeutic range.

AZD1775 has been shown to be a weak inducer of CYP1A2 in vitro with a maximum measured response between donors of 39.9% to 93.1% (at 10 µM) and 18.6% to 32.5% (at 5 µM) of the positive control omeprazole (50 µM), respectively. Given the nature of the AZD1775 dosing schedule, however, the risk of induction in the clinic is considered low.
	
Be initially vigilant when using substrates of CYP1A2 with a narrow therapeutic range.

Inhibitors or substrates of P-gp. In vitro studies have shown that AZD1775 may be a substrate and inhibitor for human P-glycoprotein (P-gp).
	
Caution should be exercised when agents that are inhibitors or substrates of P-gp are administered concomitantly with AZD1775 (see Appendix G).

Metformin
	
Metformin should be used with caution. AZD1775 has been shown to be an inhibitor of MATE1 and MATE2K transporters. A drug interaction with substrates of either transporter cannot be ruled out, the most important substrate known to date being metformin.

BCRP substrates with narrow therapeutic index
	
Recent in vitro transporter studies have shown AZD1775 to be an inhibitor of BCRP (IC₅₀ 5.1 µM). This finding is particularly relevant for drugs administered orally where exposure is normally limited by BCRP-mediated efflux, in particular some statins, such as rosuvastatin. Other drugs where the disposition is mediated via BCRP should be administered with caution, dose modification considered or substituted by an alternative drug.

7.8.3 Prohibited concomitant medications

The following treatments and the medications listed in [Appendix G](#) are prohibited while in this study. Any further questions regarding concomitant treatments should be referred to the Medical Monitor.

Prohibited Medication/Class of drug:	Additional Information
Anticancer agents other than the study medications.	If such agents are required for a patient, then the patient must first be withdrawn from the study.
Concomitant treatment with aprepitant and fosaprepitant is not allowable per protocol until further evaluation. Potent or moderate inhibitors or inducers of CYP3A4, sensitive CYP3A4 substrates, and CYP3A4 substrates with a narrow therapeutic window should be avoided until additional data on drug-drug interaction becomes available.	No formal clinical drug interaction studies have been performed with AZD1775. An exploratory assessment of the effect of aprepitant on AZD1775 exposure in oncology patients suggests that there is a drug interaction between AZD1775 and aprepitant, as exposure to AZD1775 increased by ~60% when aprepitant was co-administered with AZD1775. The observed increase in AZD1775 exposure is likely the result of CYP3A4 inhibition by aprepitant. This increase in exposure is statistically significant. At the selected MTDs, this increase may also be of clinical importance. The use of sensitive substrates of CYP3A4, such as atorvastatin, simvastatin and lovastatin are prohibited in this study (see Appendix G).
Herbal preparations/medications are not allowed throughout the study. These herbal medications include, but are not limited to: St. John's wort, kava, ephedra (ma huang), ginkgo biloba, dehydroepiandrosterone (DHEA), yohimbe, saw palmetto, and ginseng.	Patients should stop using these herbal medications 7 days prior to first dose of AZD1775.

7.8.4 Other concomitant treatment

Other medication other than that described above, which is considered necessary for the subject's safety and well-being, may be given at the discretion of the Investigator and recorded in the appropriate sections of the Case Report Form.

Patients may receive palliative radiotherapy during the trial only for local pain control, and only if in the opinion of the treating Investigator the patient does not have PD. The radiation field cannot encompass a target lesion. Radiation to a target lesion is considered PD and the patient should be removed from study treatment.

8. STATISTICAL ANALYSIS BY ASTRAZENECA

8.1 Sample size estimate

Approximately up to 172 patients may be enrolled and treated in this study (see Figure 1): 12 in the Part A safety lead-in cohort, and a maximum of up to 160 in Part B with tumour specific cohorts (ovarian [n=60], TNBC [n=50]), and SCLC [n=50]).

Approximately 12 evaluable patients will be enrolled and treated in Part A (dose escalation). Patients must complete Cycle 1 safety evaluations and must receive at least 75% of the planned Cycle 1 dose in order to be considered evaluable. Patients receiving less than 75% of the Cycle 1 dose will be replaced unless they experience a confirmed DLT. At the end of Part A, if no safety signals are reported and the PK profile appears acceptable, the Part B tumour-specific expansion cohorts will begin enrolment.

In Part B, in the TNBC and SCLC cohorts, approximately 15 biomarker positive and 15 biomarker negative patients will be enrolled and treated. An additional 20 patients in each tumour cohort may be enrolled and treated to further explore genetic profiles of interest. In addition, 60 ovarian cancer patients will be treated. Therefore, approximately up to 172 patients may be treated in the study (Part A and Part B combined).

8.2 Description of analysis sets

8.2.1 All subjects set

The All Subjects Set will include all patients who have signed the informed consent form (i.e. screening failures plus patients treated). The All Subjects Set will be used to describe the patient disposition and patient deaths on study.

8.2.2 Full analysis set

The Full Analysis Set (FAS) will include all patients who were treated with at least one non-zero dose of AZD1775. This population will be used for the primary analyses of the efficacy endpoints.

8.2.3 Safety analysis set

The Safety Analyses Set will include all patients who received at least one (non-zero) dose of AZD1775 and had at least one subsequent safety assessment.

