6.4.10 Handling of deaths

All deaths that occur during the study, or within the follow-up period after the administration of the last dose of study treatment must be reported as follows:

- Death, which is unequivocally due to disease progression, should be communicated to the study monitor at the next monitoring visit and should be documented in the eCRF module, but should not be reported as a SAE during the study.
- Where death is not clearly due to disease progression of the disease under study the AE causing the death should be reported by entering into the WBDC system as an SAE within 24 hours. The report should contain a comment regarding the co-involvement of progression of disease, if appropriate, and should assign a single primary cause of death together with any contributory causes.
- Death with an unknown cause should always be reported as a SAE but every effort should be made to establish a cause of death. A post-mortem may be helpful in the assessment of the cause of death, and if performed a copy of the post-mortem results (with translation of important parts into English) should be reported in an expedited fashion to an AstraZeneca representative within the usual timeframes.

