8.3.3 Safety analysis

In Part A DLTs will be summarised. For all parts of the study the following minimum data summaries will be presented by cohort using the Safety Analysis Set:

- TEAEs of any CTCAE grade – summarized by MedDRA preferred term and system organ class and CTCAE maximum grade
- Related TEAEs of any CTCAE grade – summarized by MedDRA preferred term and system organ class and CTCAE maximum grade
- SAEs
- Deaths summarized by primary cause
- Laboratory parameters (haematology and chemistry), vital signs, ECG data and concomitant medications including evaluations for potential DILI and QTc prolongation signals.

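### The Safety Analysis Set adds an undefined post-dose condition, so a treated Part B patient who dies before any assessment can drop out of the by-cohort safety and death tables

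*Protocol*

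**What the plan says.** Three analysis sets in the protocol bear on this point.

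- **Section 8.2.3, Safety Analysis Set:** patients who "received at least one (non-zero) dose of AZD1775 and had at least one subsequent safety assessment". This is two conditions, a dose and something after it.
- **Section 8.2.2, Full Analysis Set (FAS):** "all patients who were treated with at least one non-zero dose of AZD1775". This is one condition, and the set serves the primary efficacy analyses.
- **Section 8.2.1, All Subjects Set:** everyone who signed consent, screening failures included. "The All Subjects Set will be used to describe the patient disposition and patient deaths on study".

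Section 8.3.3 then assigns the safety tables: "For all parts of the study the following minimum data summaries will be presented by cohort using the Safety Analysis Set". Its list covers treatment-emergent events, related events, SAEs, "Deaths summarized by primary cause", laboratory data, vital signs and ECGs.

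Section 6.4.10 sets out how deaths are recorded. A death unequivocally due to progression "should be documented in the eCRF module, but should not be reported as a SAE during the study". Where progression is not clearly the cause, the event that led to death is reported as an SAE. "Death with an unknown cause should always be reported as a SAE".

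**The concern.** Whether a dosed patient has a later safety assessment is known only after dosing, and it can depend on how the patient fares. A patient who dies before the next contact fails the condition because of the outcome that the safety tables are meant to show. The same patient stays in the FAS and counts for efficacy.

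The protocol does not say what a safety assessment is. The nearest guide is the heading of section 5.2, under which laboratory tests, physical examination, tumour assessments, ECGs, vital signs, pregnancy tests and tumour markers are listed. Enquiry about adverse events and the recording of deaths are in section 6. Whether a telephone contact, an SAE report or a death record satisfies the condition is therefore left to judgement once the data are known.

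The study is descriptive, so the displayed counts and percentages are the result. In groups of about 15, one patient in or out is visible.

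**Working it through.** **1. Inputs.** Section 8.1 gives 12 patients in Part A and up to 60 ovarian, 50 TNBC and 50 SCLC patients in Part B. The plan's total reproduces: 12 + 60 + 50 + 50 = 172. The TNBC and SCLC cohorts start with about 15 biomarker-positive and 15 biomarker-negative patients each. The protocol does not state how many treated patients will lack a later assessment; 0 to 1 per cohort is assumed.

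**2. Who can fall out.** Take a dosed Part B patient who dies before the next visit.

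| Cause of death | Recorded as (6.4.10) | In FAS (8.2.2) | Described under 8.2.1 | In the 8.3.3 tables (set of 8.2.3) |
|---|---|---|---|---|
| Not clearly progression, or unknown | SAE | Yes | Yes | Only if the SAE report counts as an assessment; not stated |
| Unequivocal progression | eCRF entry, not an SAE | Yes | Yes | No SAE report exists to satisfy the condition; out, as written |

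**3. The window.** In Part B (Table 2, as far as its columns can be read in the extracted text), the adverse-event row shows Day 8 as the first scheduled entry after Day 1, and the first dosing block is Days 1 to 3. The haematology row may carry a mark under Days 2 to 4, but the column alignment is unreliable. The ECGs tied to PK sampling fall on Day 3 or Day 10, in consenting patients. The window is days, not weeks.

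In Part A, Table 1 footnote f schedules ECGs at 1, 2, 4, 6, 8 and 12 hours after the Cycle 1 Day 1 dose. A dosed patient there has a safety assessment within about an hour unless procedures are missed.

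**4. Size if it happens once.** Let a cohort have n treated patients, one death without a post-dose assessment, and no other death. All treated patients give 1/n; the set of 8.2.3 gives 0/(n − 1). Limits are exact (Clopper-Pearson) 95% upper limits. For 0 events in m patients the limit is 1 − 0.025^(1/m), for example 1 − 0.025^(1/14) = 23.2%.

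| Group | All treated | Set of 8.2.3 |
|---|---|---|
| Biomarker group, n = 15 | 1/15 = 6.7% (upper 31.9%) | 0/14 = 0% (upper 23.2%) |
| Ovarian, n = 60 | 1/60 = 1.7% (upper 8.9%) | 0/59 = 0% (upper 6.1%) |
| All, n = 172 | 1/172 = 0.6% (upper 3.2%) | 0/171 = 0% (upper 2.1%) |

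With no such patient the two sets agree. The limits only show scale; the protocol plans exact intervals for response and disease control, not for safety.

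**5. Direction.** The rate is understated only when the excluded patient had a known event. If the patient is lost with no post-dose information, inclusion changes x/(n − 1) to x/n, which lowers the event rate.

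**The case against.** The protocol's data collection works against the exclusion. A patient who stops the drug or withdraws consent is asked about adverse events (3.9.1, 3.10.2). An end-of-treatment visit and a 30-day safety follow-up, which may be by telephone, come after discontinuation (4.3, 4.3.1). Deaths not clearly due to progression are SAEs. On a natural reading many of these contacts count as assessments. Entry also requires ECOG 0 to 1 and a predicted life expectancy of at least 12 weeks. This stands: most patients who leave early would stay in the set.

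Four stronger readings are tempting, and the documents do not support them.

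- **Early deaths vanish from the report.** They do not. Section 8.2.1 describes on-study deaths on a set that contains every treated patient. What can be lost is the patient's place in the 8.3.3 tables.
- **The Part A primary safety result is compromised.** It is hardly touched. Besides the Day 1 ECGs, the DLT set in 8.2.4 keeps any patient with a DLT whatever amount of drug was taken.
- **Early event rates are biased downwards in general.** Working step 5 shows that this needs a known event in the excluded patient, and such an event would usually already be an SAE report.
- **Sections 8.2.1 and 8.3.3 contradict each other on deaths.** They can be two displays, one of all consented patients and one by cohort among treated patients. What is missing is a label that tells the reader which denominator applies.

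The objection does not remove the progression death before any post-dose assessment, or the undefined term. Nor do the documents state any benefit from the extra condition.

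**Conclusion.** The point holds for Part B, as a minor defect that costs nothing to remove. Section 8.2.3 makes membership of the safety population depend on an undefined post-dose event that the FAS does not require. As written, a treated patient who dies before any such event, most clearly of progression, can be absent from the by-cohort safety and death tables while still counting for efficacy.

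The size rests on an assumed 0 to 1 such patients per cohort, because the protocol gives no count. One such death would be visible in a biomarker group of about 15 and slight across the whole study.

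**What to change.** In section 8.2.3, delete the second condition, that is, everything in "received at least one (non-zero) dose of AZD1775 and had at least one subsequent safety assessment" from the word 'and' onwards. The Safety Analysis Set then comprises all patients with at least one non-zero dose, the same as the FAS. Use this set for the by-cohort death summary in 8.3.3.

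Keep the All Subjects Set in 8.2.1 for disposition and for describing all on-study deaths. Restricting it to disposition would lose deaths between consent and first dose. State the denominator on each display.

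The cost is one deleted clause and a label on each death display. No new data, visits or analyses are needed.

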8.2.4 Dose-limiting analysis set

The DLT analysis set will include all patients in the Part A safety lead-in cohort who received at least 75% of the AZD1775 dose and completed the minimum safety evaluation requirements during the first 21 days of treatment or who experienced a DLT during the first 21 days of treatment regardless of the amount of drug received.

The patients in the DLT analysis set will be used for the determination of safety of the dose and schedule of AZD1775 in Part A.

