7.2 Dose and treatment regimens

AZD1775 will be taken by mouth in approximate 12 hour intervals over 3 days at the start of week 1 and 2 of each 21-day cycle (Days 1-3 and 8-10), for a total of 12 doses with each cycle (see [Figure 2](#)). Mandatory prophylactic anti-emetic therapy will be administered as described in Section [6.8.3.2](#).

AZD1775 should be taken with 8 ounces of water approximately 2 hours before and again 2 hours after food. If BID dosing and a patient misses one of the two daily doses according to schedule, the dose should be taken as soon as possible, but not more than 6 hours after the missed dose was scheduled. If greater than 6 hours, the missed dose should be skipped and the patient should take the next dose when scheduled.

[figure not shown]
If vomiting occurs after a patient takes the AZD1775 dose, the patient should be instructed not to retake the dose, but to wait until the next scheduled dose of AZD1775. If no dose is scheduled for the following day, the dose will not be 'made up'. If vomiting persists, the patient should contact the Investigator.

AZD1775 dosing compliance should be reviewed with the patient at the beginning of each new treatment cycle when study drug is dispensed. All patients will be required to complete a dosing diary, which must be returned to the clinic for review at each visit. The patient should be instructed to record each date and time the dose(s) were taken on the dosing diary. If a dose is missed, the reason must be noted in the diary. A copy of the dosing diary is provided in the study reference materials.

Patients should be advised to return any unused AZD1775 in the original bottles, in addition to returning any empty bottles.

Figure 2 **21-day cycle**
AZD1775 dosing schedule, 21-day cycle

Day of Cycle

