7.2.1 Part A: Safety lead-in cohort (closed to enrolment – October 2015)

The safety and tolerability of AZD1775 monotherapy in patients with advanced solid tumours will be assessed in a safety lead-in cohort. Patients in the safety lead-in will receive the planned dose and schedule for the study, 200 mg PO BID for 3 days at the start of weeks 1 and 2 of each 21-day cycle. Pharmacokinetic and pharmacodynamics samples will be collected from all Part A patients (see Section 5.3.1). During the safety lead-in, the AZD1775 starting dose was reduced to 175 mg BID because 200 mg BID was not well-tolerated. Adverse events (AEs) associated with AZD1775, and DLTs observed during the safety lead-in included diarrhoea, vomiting and anaemia. In addition to reducing the starting dose of AZD1775, mandatory anti-emetic prophylaxis has been instituted (see Section 6.8.3.2). The Part A safety lead-in patient enrolment has been completed.

After approximately 12 evaluable patients have completed Cycle 1, a Safety Review Team (SRT [see Section 10.7]) will review the accumulated safety and tolerability data of the AZD1775 monotherapy dose and schedule. Patients must complete Cycle 1 safety evaluations which will conclude on Cycle 2 Day 1, and must receive at least 75% of the planned Cycle 1 dose to be considered evaluable. Patients receiving less than 75% of Cycle 1 dose will be replaced unless they experienced a confirmed DLT by the SRT.

At the end of Part A, if no safety signals are reported and the PK profile appears acceptable, the Part B tumour specific expansion cohorts will begin enrolment.

Dose-limiting toxicities thought to be related to the study drug during the safety lead-in phase will be defined as any of the following toxicities not attributable to the disease or disease-related processes under investigation, that occur from the first dose of study treatment up to the last day of Cycle 1 (first 21 days) and that meets at least 1 of the haematological or non-haematological criteria below:

1. Haematological toxicity \geq Grade 4 present for more than 7 days including:
 - Infection with febrile neutropenia
2. Grade 3 thrombocytopenia associated with Grade \geq 2 bleeding
3. Non-haematological toxicity \geq Grade 3
4. Grade \geq 3 total bilirubin, hepatic transaminase (alanine aminotransferase [ALT] or aspartate aminotransferase [AST]) or alkaline phosphatase (ALP) lasting $>$ 48 hours.

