5. Changes in liver function tests (LFTs) consistent with the definition of Hy's Law (see Appendix C).
6. Any other toxicity that is clinically significant and/or unacceptable that does not respond to supportive care, results in a disruption of dosing schedule of more than

7 days, or is judged to be a DLT by the Investigator in collaboration with the Medical Monitor.

A DLT excludes:

- Alopecia of any grade
- Isolated laboratory changes of any grade without clinical sequelae or clinical significance

If appropriate the DLT observation period can be expanded by up to 2 weeks in case of treatment delay due to study drug-related adverse events. Treatment will be considered non-tolerated if 2 or more of the first 6 evaluable patients experience a DLT in the safety lead-in cohort. If the initial dose or schedule of the treatment is not tolerated, patient enrolment to the treatment will be stopped and either the schedule will be taken no further or the dose level or schedule of AZD1775 may be adjusted to evaluate safety in a second 6 patient cohort at the next lower dose level or revised schedule. The DLT criteria apply only to the safety lead-in patients during Cycle 1. Safety lead-in patients continuing treatment beyond Cycle 1 will have dose modifications applied according to Section 6.8.

If fewer than 2 out of the first 6 evaluable patients experience a DLT, enrolment will continue to approximately 12 evaluable patients to further evaluate safety. If 4 or more of 12 evaluable patients experience a DLT then the treatment will be considered not tolerated.

Investigators will be notified in a timely manner of any safety outcomes so that they may notify their Institutional Review Boards (IRBs).

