8.5 Timing of analyses

8.5.1 Part A: safety lead-in cohort

A formal analysis of safety data will take place after 12 evaluable patients have completed the Cycle 1 DLT evaluation.

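### The DLT analysis set in 8.2.4 stops at Day 21, while 7.2.1 lets DLT observation run to Day 35, so a late DLT in an under-dosed Part A patient drops out

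*Protocol*

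**What the plan says.** Section 8.2.4 gives two routes into the DLT analysis set. The first is at least 75% of the AZD1775 dose together with the minimum safety evaluations in the first 21 days. The second covers patients "who experienced a DLT during the first 21 days of treatment regardless of the amount of drug received". The section says this set is the one used to judge the safety of the Part A dose and schedule.

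Section 7.2.1 starts from the same window, counting toxicities "that occur from the first dose of study treatment up to the last day of Cycle 1 (first 21 days"). It then adds that, if appropriate, "the DLT observation period can be expanded by up to 2 weeks in case of treatment delay due to study drug-related adverse events". Section 8.2.4 does not mention this extension.

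On under-dosing, 7.2.1 says "Patients receiving less than 75% of Cycle 1 dose will be replaced unless they experienced a confirmed DLT by the SRT". Section 8.1 repeats the rule: "Patients receiving less than 75% of the Cycle 1 dose will be replaced unless they experience a confirmed DLT". Neither sentence limits the exception to 21 days.

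On timing, 8.5.1 says "A formal analysis of safety data will take place after 12 evaluable patients have completed the Cycle 1 DLT evaluation". Section 8.3.3 calls for a summary of Part A DLTs but does not name the set for it.

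**The concern.** The extension in 7.2.1 exists so that a DLT appearing after a drug-related delay is still observed. The analysis set has no place for such a DLT if the patient was also under-dosed, and drug-related delay and under-dosing tend to occur in the same patients. Read literally, the set discards an event that another operative section was written to capture.

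The loss is one-sided: the patient left out always has a DLT. The count that triggers the Part A analysis in 8.5.1 can also include someone whom the analysis set then omits. The protocol itself fixes both the set and its use, so a SAP that followed 8.2.4 would carry the gap forward.

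**Working it through.** The protocol gives no DLT rate or error rate to reproduce. The check compares the rules and then works out what one omitted patient does to the reported rate.

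**Inputs**

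- Base window: 21 days (7.2.1 and 8.2.4). Extension: up to 14 days (7.2.1).
- Planned doses: "for a total of 12 doses with each cycle" (7.2).
- Dose threshold: 75% (7.2.1, 8.1, 8.2.4).
- A dose missed by more than 6 hours is skipped (7.2).
- DLT criterion 6 includes a clinically significant toxicity that "results in a disruption of dosing schedule of more than" 7 days (7.2.1).
- Cohort sizes: 6 and about 12 evaluable patients (7.2.1).

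**Where the gap lies**

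- Extended window: 21 + 14 = Day 35. The uncovered days are 22 to 35.
- Dose threshold: 0.75 × 12 = 9 doses, so under-dosed means 8 or fewer (8/12 = 67%).

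| Patient with under 75% of the Cycle 1 dose | 7.2.1 and 8.1 | 8.2.4 |
|---|---|---|
| DLT by Day 21 | kept | in the set |
| First confirmed DLT on Days 22–35, observation extended | kept | not in the set |
| No DLT | replaced | not in the set |

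Only the middle row conflicts. Patients at 75% or more who complete the evaluations enter by the first route.

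**A case that reaches the gap**

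1. A drug-related adverse event that is not itself a DLT moves the Day 8 block to Day 15: 15 − 8 = 7 days. That is not more than 7, so criterion 6 is not met by the delay.
2. Two doses in each block are missed by more than 6 hours and skipped: 12 − 4 = 8 doses, or 67%.
3. Observation is extended, and a first DLT is confirmed on Day 25.

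The patient never reaches 75%, so it does not matter whether the 21-day phrase in 8.2.4 also limits the dose test. A longer hold does not give an example: a toxicity that holds the second block beyond 7 days meets criterion 6 by about Day 16, and the patient enters the set through the DLT route.

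**Size per omitted patient**

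With x DLTs among n patients, leaving out one DLT patient changes the rate by

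x/n − (x − 1)/(n − 1) = (n − x) / [n(n − 1)],

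which is positive whenever x < n.

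| n | x | All counted | One omitted | Drop (points) |
|---|---|---|---|---|
| 12 | 1 | 8.3% | 0/11 = 0% | 11/132 = 8.3 |
| 12 | 2 | 16.7% | 1/11 = 9.1% | 10/132 = 7.6 |
| 12 | 3 | 25.0% | 2/11 = 18.2% | 9/132 = 6.8 |
| 12 | 4 | 33.3% | 3/11 = 27.3% | 8/132 = 6.1 |
| 6 | 1 | 16.7% | 0/5 = 0% | 5/30 = 16.7 |
| 6 | 2 | 33.3% | 1/5 = 20.0% | 4/30 = 13.3 |

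These are reported rates. The tolerability rules in 7.2.1 (2 or more of 6; 4 or more of 12) are stated on evaluable patients and do not move.

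**The case against.** The strongest reply is that 8.2.4 only repeats the shorthand of 7.2.1. That section also defines DLTs over the first 21 days and confines the criteria to Cycle 1 before allowing the extension, so a reader could stretch the phrase in 8.2.4 in the same way. That reading is possible, but nothing in 8.2.4 points to the extension, and an analysis set should not depend on a reader importing it.

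Second, neither 7.2.1 nor 8.1 says outright that the under-dosed patient with a DLT is evaluable; they say the patient is not replaced. This stands as a point of wording: evaluability is an inference. It is a sound one, because the sentence is the exception to the 75% condition, and 8.2.4 itself waives the dose test for patients with a DLT.

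Third, the gap is narrow. Many toxicities that delay dosing are already DLTs: non-haematological Grade 3 or above, disruption beyond 7 days, or anything the Investigator and Medical Monitor judge to be one. The worked case needs four skipped doses as well as a delay and a late first DLT, and nothing in the protocol suggests that it happened. All of this stands and limits the importance of the point.

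Fourth, Part A is closed, the 175 mg dose for Part B is set (7.2.2), and 6.8 says DLT evaluation does not apply to Part B. The event would also still appear in the TEAE summary, and in the SAE summary where serious, on the Safety Analysis Set. This stands too, and it is why the point concerns reporting only.

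**Conclusion.** The point holds as a minor inconsistency between operative sections. As written, 8.2.4 excludes an under-dosed Part A patient whose first confirmed DLT falls on Days 22 to 35 of an extended observation period, although 7.2.1 and 8.1 keep that patient. The error runs in one direction, toward a lower reported DLT rate, by 6.1 to 8.3 points per affected patient among 12 (for one to four DLTs) and by 13.3 to 16.7 points among 6 (for one or two).

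The conclusion rests on a literal reading of the 21-day limit, on the inference that a patient not replaced is evaluable, and on the DLT summary being run on the 8.2.4 set. If no Part A patient fits the description, no reported figure changes.

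**What to change.** In 8.2.4, replace both references to the first 21 days with the DLT observation period, including any extension under 7.2.1. Write the dose test as at least 75% of the planned Cycle 1 dose, as 7.2.1 and 8.1 do, so that a longer window cannot count Cycle 2 doses toward it. Report the Part A DLT summary on that set, consistent with the Safety Review Team's classification, and state how many patients enter only through the extension, even if none do.

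The cost is one reworded sentence and a check of about 12 Part A patients. No new data are needed, and nothing changes for patients whose observation was not extended.
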